# 7.1.3. Iron Absorption Substudy (See Table 3)

Iron absorption subjects will be treated and monitored in an identical manner as the rest of the study population.

Subjects consenting to participate in the iron absorption substudy will receive the stable iron isotope Fe orally (approximately 4 mg as ferrous sulfate) on two occasions; once prior to starting PTG-300 (i.e., after the phlebotomy performed during the Screening period, Iron Absorption A), and a second dose after 4 to 6 weeks after starting PTG-300 (i.e., post-treatment; Iron Absorption B). The post-treatment Iron Absorption B administration will occur approximately 24 hours following a PTG-300 dose.

Subjects will receive Fe orally after an overnight fast of at least 8 hours. Subjects should fast for approximately 4 hours after the Fe dose. Blood samples will be collected at 0, 4, 8, 12, and 24 hours for measurement of Fe levels and for measurement of iron parameters—serum iron, serum ferritin, transferrin, and TSAT. Additional blood samples will be obtained at 0, 4, 8, 12, and 24 hours following Iron Absorption B for measurement of PTG-300 concentrations.

Food will be allowed starting 4 hours after the Fe administration. Subjects will be monitored in the study center for at least 12 hours, after which subjects may stay overnight or be discharged home (at the discretion of the subject and investigator) and return the next day (approximately 24 hours following Fe administration).

# 7.1.4. Post-Treatment / Early Termination Safety Follow-Up (Week 29)

Subjects who complete the treatment or who discontinue treatment early will undergo Visit 8/end of treatment (EOT) assessments as well as follow-up safety evaluations approximately 4 weeks after the last dose of study drug (Visit 9/end of study [EOS]).

# 7.2. Safety

Safety will be monitored carefully throughout the study.

Safety measures (including but not limited to physical examinations, clinical laboratory tests, complete blood count [CBC], vital signs, electrocardiograms [ECGs], adverse event monitoring [AEs], and concomitant medications) will be evaluated and recorded over the course of the study according to the schedule of assessments (Table 2). Clinical sites may conduct local laboratory tests if required by site procedures.

Any AE that emerges from the time the subject signs an informed consent form (ICF) until Study Exit will be recorded and reported. Safety will be assessed using National Institutes of Health (NIH) Common Terminology Criteria for Adverse Events (CTCAE) v5.0 criteria. It is recommended that prior to reducing the dose the dosing interval is increased to 2 weeks to alleviate any safety concerns.

# 7.2.1. Safety Criteria for Dose Interval Increase or Dose Reduction

The presence of at least one of the following criteria will require a dose reduction:

- CTCAE Grade 3 hematological toxicity or worsening of ≥2 grades in hematological parameters not clearly resulting from the underlying disease and/or without a clear-cut alternative that does not respond adequately to medical therapy.
- CTCAE Grade 3 non-hematological toxicities not clearly resulting from the underlying disease and/or without a clear-cut alternative that does not respond adequately to medical therapy.
- Treatment-related decrease of Hgb from baseline >20% or Grade 2 anemia, whichever is lesser, confirmed by a repeat value and not due to phlebotomy. Prior to resumption of PTG-300 at a reduced dose a follow-up Hgb should be assessed to confirm that Hgb has stabilized or improved to Grade 1.
- Investigator determines that the subject has experienced a clinically significant decrease in Hgb due to PTG-300.

If a treatment-related increase in aspartate aminotransferase (AST) or alanine aminotransferase (ALT) >3 × upper limit of normal (ULN) is seen, dosing with PTG-300 should be held, with resumption at a reduced dose if the AST and/or ALT levels return to baseline within 14 days; if the levels do not return to baseline within 14 days, an MRI should be conducted to assess whether there is an increase in iron accumulation.

Dose reduction has two steps. Initially subjects continue to receive the same dose of PTG-300 but the dosing frequency is reduced from twice weekly to weekly, or from weekly to every 2 weeks. If the subject continues to meet criteria for dose reduction, the dose is then decreased one dose level.

# 7.2.2. PTG-300 Discontinuation or Stopping

The following are stopping criteria for an individual subject and will result in **discontinuation** of the subject from further treatment with study drug:

- Any CTCAE Grade 4 hematological or non-hematological toxicity not clearly resulting from the underlying disease and/or without a clear-cut alternative.
- CTCAE Grade 3 hematological toxicity or worsening of ≥2 grades in hematological parameters not clearly resulting from the underlying disease and/or without a clear-cut alternative persists over 7 days after adequate PTG-300 dose decrease.
- CTCAE Grade 3 non-hematological toxicities not clearly resulting from the underlying disease and/or without a clear-cut alternative explanation that do not improve within 14 days with maximal medical therapy and adequate PTG-300 dose decrease.
- When the Investigator in consultation with the medical monitor (MM) considers that is in the subject's best interest to discontinue treatment with PTG-300 (i.e., persistent, worsening or recurrent AEs).
- If a subject requires a dose reduction below 10 mg administered every 2 weeks.

- ALT, AST >5 × ULN and rising.
- ALT, AST remains >5 × ULN with no change in total bilirubin for more than 2 weeks.
- A worsening of clinical symptoms with no other acceptable explanation.
- The product meets Hy's Law:
  - Any test showing an increase of serum ALT >3 × ULN or >2 × ULN total bilirubin should be repeated within 48 to 72 hours for ALT, AST, alkaline phosphatase (ALP), and total bilirubin. If the repeat value for ALT or total bilirubin is unchanged or indicates decreasing activity, monitoring should continue at weekly intervals until the results are acceptable or normalized.
- Evidence of clinically meaningful increased iron accumulation in liver from baseline.

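### The mandatory stop for ALT/AST staying above 5 × ULN falls away when bilirubin rises, and the repeat-test rule lets one stable value excuse a rising one

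*Combined protocol and SAP*

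**What the plan says.** Section 7.2.2 opens its list with "The following are stopping criteria for an individual subject and will result in" discontinuation of study drug. Ten bullets follow, and the synopsis repeats the list. Those that bear on the liver are:

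- ALT/AST above 5 × ULN and rising, with no bilirubin condition.
- ALT/AST remaining above 5 × "ULN with no change in total bilirubin for more than 2 weeks". No size is given for a change in bilirubin.
- "The product meets Hy's Law". The only text beneath it is a testing instruction. An ALT above 3 × ULN, or a total bilirubin above 2 × ULN, "should be repeated within 48 to 72 hours for ALT, AST, alkaline phosphatase (ALP), and total bilirubin". It continues: "If the repeat value for ALT or total bilirubin is unchanged or indicates decreasing activity, monitoring should continue at weekly intervals". No combined ALT-and-bilirubin threshold is written, and no action is stated for a repeat value that rises.
- "Evidence of clinically meaningful increased iron accumulation in liver from baseline". The synopsis omits the clinically-meaningful qualifier.

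Three more general bullets can also apply:

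- Grade 3 non-hematological toxicities "that do not improve within 14 days with maximal medical therapy and adequate PTG-300 dose decrease", subject to a condition on other causes.
- "A worsening of clinical symptoms with no other acceptable explanation".
- A best-interest stop by the investigator in consultation with the medical monitor.

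Section 7.2.1 separately holds dosing for a treatment-related AST or ALT above 3 × ULN. It offers resumption at a reduced dose if levels return to baseline within 14 days, and otherwise calls for an MRI to look for iron accumulation. Section 8.3 allows withdrawal in the subject's interest.

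**The concern.** A stopping rule for persistent enzyme elevation should become no weaker as the liver picture worsens. As worded, this one does. A subject whose enzymes stay high with flat bilirubin must stop. A subject with the same enzymes and rising bilirubin no longer meets that bullet. The repeat-test instruction has a related fault: because it joins ALT and bilirubin with *or*, one steady value is enough to move the subject to weekly monitoring while the other climbs.

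What is at stake is protection of the individual subject. Section 5.2.1 reports hepatocellular necrosis in rats, possibly secondary to excess liver iron, although at 25 mg/kg, above the 26-week rat NOAEL of 10 mg/kg. Subjects may self-inject at home, and after Day 1 the scheduled chemistry is at Week 5 and every 4 weeks from then on, so the written retest rule matters between visits. Deciding whether an enzyme rise comes from the drug or the disease is also hard here, because section 5.1 lists cirrhosis and liver cancer among the complications of iron excess. A stop resting on laboratory values and time avoids that judgement.

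**Working it through.** The plan gives no figure to reproduce on this point. The check applies the written rules literally.

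**Step 1. The two enzyme bullets, for ALT/AST above 5 × ULN lasting more than 2 weeks.**

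| ALT/AST trend | Total bilirubin | Above 5 × and rising | Persistent, bilirubin unchanged | Either met |
|---|---|---|---|---|
| Rising | Unchanged | Yes | Yes | Yes |
| Rising | Rising | Yes | No | Yes |
| Flat | Unchanged | No | Yes | Yes |
| Flat | Rising | No | No | **No** |
| Falling, still above 5 × | Unchanged | No | Yes | Yes |
| Falling, still above 5 × | Rising | No | No | **No** |

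Two of six combinations are uncovered, both with rising bilirubin.

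**Step 2. Worked cases (values in × ULN, chosen for illustration).** The documents do not reproduce the CTCAE cut-offs, so I assume that 6 × ULN is Grade 3. For the Hy's Law bullet I assume a combined reading of ALT above 3 with bilirubin above 2.

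- *Case A:* ALT steady at 6 for 21 days, bilirubin flat at 0.8. Since 21 > 14 days and bilirubin is unchanged, the persistent-elevation bullet is met: 1 of 10 bullets on values and time alone.
- *Case B:* ALT steady at 6 for 21 days, bilirubin rising from 0.8 to 1.8. ALT is not rising, bilirubin has changed, and 1.8 < 2: 0 of 10 on values and time alone. Five of 10 can still apply with further facts: Grade 3 non-hematological, investigator/medical monitor, a needed dose below 10 mg every 2 weeks, symptoms, and liver iron. If 6 × ULN were graded below 3, the first and third of these fall away, leaving 3 of 10.

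These counts describe rules, not risk.

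**Step 3. The repeat-test sentence.** *Case C:* ALT 4 then 4, bilirubin 1.2 then 1.9 on the repeat. ALT is unchanged, so the *or* condition is satisfied and the next test may be 7 days later. Requiring all three values to be unchanged or decreasing puts the next draw at 2–3 days, which is 7 − 3 = 4 to 7 − 2 = 5 days sooner. Bilirubin is below 2 at both draws, so the assumed Hy's Law criterion would not stop this subject; only the retest change helps.

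**Step 4. What still covers Case B.**

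| Route | What it depends on |
|---|---|
| 7.2.1 hold above 3 × ULN | Judged treatment-related; a hold, not a discontinuation |
| 7.2.1 Grade 3 dose reduction | Grading, cause, inadequate response to medical therapy |
| 7.2.2 Grade 3 non-hematological stop | Grading, cause, maximal medical therapy, adequate dose decrease |
| 7.2.2 dose-floor stop | A required reduction below 10 mg every 2 weeks |
| 7.2.2 symptoms | Clinical worsening without another acceptable explanation |
| 7.2.2 liver iron | MRI evidence of an increase |
| 7.2.2 investigator/medical monitor; 8.3 | Discretion |

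The Grade 3 stop's 14-day clock is no slower than the rule that drops out; its preconditions are what differ. If a held subject's MRI shows no iron increase, 7.2.1 states no next step.

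**The case against.** The strongest reply is that in the main case the subject is already off drug. The 7.2.1 hold starts at 3 × ULN, below the 5 × threshold, and has no bilirubin condition. Resumption is offered only on return to baseline within 14 days, so a Case B subject whose elevation is treatment-related has no written route back to dosing. That stands, and it sets the size of the point. Such a hold may also satisfy the dose-decrease condition of the Grade 3 stop, and the investigator/medical-monitor bullet names persistent or worsening events. Table 2, note g, allows additional tests as needed.

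A second reply is that the bullets form a natural ladder: rising enzymes, persistent enzymes without bilirubin involvement, then enzymes with bilirubin under Hy's Law. On that reading only bilirubin that has risen but not reached the Hy's Law level is missed. This also stands; the uncovered band is an intermediate one. The sponsor may equally have meant that flat bilirubin does not excuse persistence, in which case the amended wording simply states the intent.

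A reader might infer that a subject with rising bilirubin could be left on drug with no safeguard. Step 4 shows otherwise. A reader might also infer that the Hy's Law bullet protects no individual because it speaks of the product. The list's opening makes it a per-subject criterion, so the intent is clear; what is missing is a written definition. Finally, a literal reading would let a move from 0.8 to 0.9 × ULN switch the persistence rule off. That shows the lack of a tolerance, but it does not show that sites would apply the rule that way.

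**Conclusion.** The wording fault is real in both places it appears. With ALT/AST flat or slowly falling but above 5 × ULN for more than 2 weeks, and bilirubin rising but below a Hy's Law level, no stop rests on laboratory values and time alone. The weekly-monitoring sentence likewise tolerates one rising value.

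The consequence is narrow. It falls mainly on elevations judged not treatment-related, and on subjects who are held but never formally discontinued. The documents give no expected frequency, and the risk looks low: entry excludes ALT/AST at or above 2.5 × ULN and direct bilirubin above 1.5 × ULN, and no hepatic event is listed among the events in more than 5% of the 63 β-thalassemia subjects. The finding does not rest on the Hy's Law wording, which needs clarifying only. It assumes a literal reading of the persistence bullet and, for the worked cases, the grading and Hy's Law assumptions in Step 2. It merits correction at the next amendment as a matter of subject protection.

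**What to change.** In section 7.2.2 and the synopsis:

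- Reword the persistence stop so that ALT or AST remaining above 5 × ULN for more than 2 weeks requires discontinuation regardless of total bilirubin. Cases A and B then both stop once 14 days are exceeded.
- Allow weekly monitoring after a repeat test only if ALT, AST and total bilirubin are all unchanged or decreasing. Otherwise repeat again within 48–72 hours.
- As an accompanying clarification, reword the Hy's Law bullet to refer to the subject meeting Hy's Law criteria, with the combined thresholds set by the sponsor's safety physicians.

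The cost is a few lines in an amendment, with the IRB/IEC re-approval that section 16.5.1 requires, and an occasional unscheduled draw when a value is still rising on repeat. No scheduled visits are added, and efficacy and power are unaffected.

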# 7.3. Number of Subjects

Approximately 28 subjects will be enrolled in the study to ensure a total of 20 subjects complete at least 16 weeks of treatment. Approximately 6 subjects will participate in the iron absorption substudy.

# 7.4. Treatment Assignment

This is an open-label study with all subjects receiving PTG-300.

# 7.5. Dose Adjustment Criteria

The investigator may increase a subject's dose up to 80 mg per week based on lack of pharmacodynamic (TSAT) response and acceptable safety. The starting dose and/or the dosing regimen will be evaluated and modified to enhance clinical benefit (see Section 7.1.2).

Based on pre-defined safety criteria (see Section 7.2.1), a subject's dosing frequency and dose may be reduced.

# 7.6. Endpoints

**Baseline Definition:** The serum ferritin level and TSAT obtained during Screening will be used as baseline.

## **7.6.1.** Efficacy

- Change from baseline in serum ferritin.
- Duration of time that serum ferritin is below baseline measurement.
- Change from baseline in TSAT.
- Duration of time that TSAT is below baseline measurement.
- Time to first phlebotomy after dosing.

- Change in frequency of phlebotomies based on historical phlebotomy data (24 weeks).
- Proportion of subjects who achieve phlebotomy independence.
- Additional Endpoints:
  - SF-36
  - PGI-C
  - Change in iron absorption following the administration of PTG-300. (For subjects completing iron absorption substudy.)
  - PTG-300 pharmacokinetics: PTG-300 concentration as a function of dose and time since last dose.
  - PD: Change from baseline in serum iron, transferrin and sTfR.
  - Change from baseline in LIC assessed by MRI.
  - Incidence of ADA.

# **7.6.2.** Safety

Safety is assessed using NIH CTCAE v5.0 criteria.

- Tabulate frequency of treatment-emergent adverse events (TEAEs) and SAEs; treatment-related TEAEs and SAEs; TEAEs leading to study discontinuation.
- Summarize vital signs, safety laboratory assessments, ECGs, and physical examination findings.

## 8. SELECTION AND WITHDRAWAL OF SUBJECTS

# 8.1. Subject Inclusion Criteria

Subjects must meet ALL of the following inclusion criteria to be enrolled:

- 1. Male and female subjects aged 18 years or older.
- 2. Have a confirmed diagnosis of HFE-related hereditary hemochromatosis with prior genotype testing.
- 3. Documented stable phlebotomy for ≥6 months prior to screening; with a phlebotomy frequency of at least 0.25 per month (e.g., received at least three phlebotomies over the previous 12 months, or at least four phlebotomies over the previous 15 months) and a phlebotomy frequency of less than 1 per month.
- 4. Screening hemoglobin >11.5 g/dL.
- 5. Serum ferritin <300 ng/mL at screening (before screening phlebotomy).
- 6. Women of childbearing potential (WOCBP) and men with partners of childbearing potential agree to use a highly effective contraceptive measure (based on the Clinical Trials Facilitation Group [CTFG]) during the duration of the study and for 28 days after the last dose of study drug in the case of women and 90 days after the last dose of study drug in the case of men.
- 7. Subject understands the study procedures, is willing and able to adhere to study requirements and agrees to participate in the study by giving written informed consent.

# 8.2. Subject Exclusion Criteria

Subjects must meet NONE of the following exclusion criteria to be enrolled.

- 1. Clinically meaningful laboratory abnormalities at Screening including, but not limited to:
  - a. Absolute neutrophil count <1000/µL
  - b. Platelet count  $<100,000/\mu L$
  - c. Estimated Glomerular Filtration Rate (eGFR) <40 mL/min/1.73 m^2
  - d. Alanine aminotransferase (ALT) or aspartate aminotransferase (AST)  $\geq$ 2.5 × upper limit of normal (ULN) or direct bilirubin >1.5 × ULN
  - e. C-reactive protein (CRP)  $\geq$  5.0 mg/L.
- 2. Receiving iron chelation therapy.
- 3. Receiving erythrocytapheresis.
- 4. Pregnant or lactating females.
- 5. Infection requiring hospitalization or intravenous antimicrobial therapy, or opportunistic infection within 3 months of dosing; any infection requiring antimicrobial therapy within 4 weeks of dosing. Prophylactic antibiotics are allowed.
- 6. Any serious or unstable medical or psychiatric condition that would prevent (as judged by the Investigator) the subject from properly providing informed consent or any

condition which would jeopardize compliance with the study or assessment of the study's endpoints.

- 7. Organ damage from iron overload, that (as judged by the Investigator) may be worsened by participation in this trial.
- 8. Known primary or secondary immunodeficiency.
- 9. Known history of autoimmune/inflammatory diseases.
- 10. Positive for active hepatitis B or hepatitis C or known human immunodeficiency virus (HIV) infection. Active hepatitis B is defined as a known positive hepatitis B surface antigen (HBsAg) result. Active hepatitis C is defined by a positive hep C Ab result and known quantitative hepatitis C virus (HCV) ribonucleic acid (RNA) results greater than the lower level of detection of the assay. Subjects who have a history of HCV infection but have documented sustained virologic response 12 weeks after HCV therapy (SVR12) are eligible.
- 11. Any surgical procedure requiring general anesthesia within 1 month prior to screening or planned elective surgery during the study (within 3 months for joint replacement surgery).
- 12. History of invasive malignancies within the last 2 years, except non-melanoma skin cancer and localized cured prostate cancer, cervical cancer, and ductal carcinoma in situ (DCIS).
- 13. Current or recent history of alcohol dependence or illicit drug use within 6 months prior to screening.
- 14. Subject is unable to give informed consent.
- 15. Receipt of an investigational agent within 30 days of Screening.

# 8.3. Subject Withdrawal Criteria

Subjects may choose to withdraw at any time.

Subjects should be withdrawn if the Investigator or Sponsor thinks withdrawal is in the subject's best interest.

A subject must be withdrawn if the subject becomes pregnant, is non-compliant with study procedures so that assessment of safety and efficacy are significantly compromised, starts an experimental therapy for HH, or meets dose stopping criteria (Section 7.2.2).

## 9. STUDY PROCEDURES

Study procedures should be completed as designated in the Schedules of Assessments (Table 2 and Table 3).

 Table 2:
 Schedule of Assessments for Study PTG-300-06

Assessment	Screeninga	24 Weeks of PTG-300 Treatment								Visit 9/EOS Safety Follow-Up	
		Vis (W		Visit 2	Visit 3	Visit 4	Visit 5	Visit 6	Visit 7	Visit 8/EOT	~4 Wks After Last Dose c (~Wk 29)
Study Week b	D -21 to -1	D 1	D2	(Wk 3 [D15])	(Wk 5 [D29])	(Wk 9 [D57])	(Wk 13 [D85])	(Wk 17 [D113])	(Wk 21 [D141])	(Wk 25 [D169])	
Informed Consent & HIPAA Authorization d	X										
Significant medical history	X										
Phlebotomy history (for up to previous 15 months)	X										
Inclusion/exclusion criteria	X										
Demographics	X										
Physical examination (including weight)	X										X
Height	X										
Vital signs	X	X	X		X	X	X	X	X	X	X
12-lead ECG	X	X	X			X		X		X	X
MRI (liver iron concentration)	X									X	
Hepatitis B & C screen	X										
Phlebotomy	Xe										
Phlebotomy evaluation f					X	X	X	X	X	X	
Concomitant medications	X	X			X	X	X	X	X	X	X
Adverse events g	X	X	X	X	X	X	X	X	X	X	X
Serum pregnancy testh	X										X
Urine pregnancy test h		X			X	X	X	X	X	X	
CRP	X					X		X		X	

Assessment	Screeninga	24 Weeks of PTG-300 Treatment							Visit 9/EOS Safety Follow-Up		
		l l	it 1 k 1)	Visit 2	Visit 3	Visit 4	Visit 5	Visit 6	Visit 7	Visit 8/EOT	~4 Wks After Last
Study Week b	D -21 to -1	D1	D2	(Wk 3 [D15])	(Wk 5 [D29])	(Wk 9 [D57])	(Wk 13 [D85])	(Wk 17 [D113])	(Wk 21 [D141])	(Wk 25 [D169])	Dose c (~Wk 29)
Iron Absorption Substudyi	X				Xi						
Study drug administration j			Weekly								
Clinical laboratory tests k	X	X			X k	X	X k	X	X k	X	X
CBC	X	X			X	X	X	X	X	X	X
Iron parameters: Serum iron, transferrin saturation (TSAT), serum ferritin, transferrin l,m	X	X	X	X	X	X	X	X	X	X	
Soluble transferrin receptor (sTfR)	X					X				X	
Hepcidin	X					X				X	
PK blood samples for measurement of PTG-300 concentration m		Xl	X	X	X	X	X¹	X	X	X	X
ADA		X				X		X		X	X
SF-36	X									X	
PGI-C						X		X		X	
Assess study drug compliance					X	X	X	X	X	X	

Abbreviations: ADA = anti-drug antibody, CBC = complete blood count, CRP = C-reactive protein, D = day, ECG = electrocardiogram, EOS = end of study, EOT = end of treatment, HIPAA = Health Insurance Portability and Accountability Act, MRI = magnetic resonance imaging, PGI-C = Patient's Global Impression of Change, SF-36 = 36-Item Short Form Health Survey, sTfR = soluble transferrin receptor, TSAT = transferrin saturation.

